12.2.1 Adverse Events

All AEs occurring during the study will be recorded and classified on the basis of Medical Dictionary for Regulatory Activities (MedDRA) terminology. Descriptions of AEs will include the date of onset, the date the AE ended, the severity of the AE, the relationship to study drug, the action taken regarding study drug usage, the action taken to treat the AE, and the outcome.

Treatment-emergent adverse events (TEAEs) are those events with an onset on or after the date of the first study drug application. All reported TEAEs will be summarized by the number of subjects reporting TEAEs, system organ class, preferred term, severity, seriousness, and relationship to study drug.

Adverse events will be summarized by treatment group and severity. Each subject will be counted only once within a system organ class or a preferred term by using the AEs with the highest severity within each category.

Adverse events will be summarized by treatment group and relationship to study drug. Each subject will be counted only once within a system organ class or a preferred term by using the AEs with the greatest relationship within each category.

The percentage of subjects reporting AEs will be summarized by treatment group for AEs occurring in at least 5% of subjects (in any treatment group). The percentage of subjects for each treatment group will be compared using a Fisher's Exact test.

All information pertaining to AEs noted during the study will be listed by subject, detailing the verbatim term given by the investigator, preferred term, system organ class, start date, stop date, severity, action taken, and drug relatedness. The AE onset will also be shown relative (in number of days) to the day of initial dose of the randomized study drug.

Serious adverse events will be tabulated by subject within treatment groups.

In addition, a list of subjects who discontinued from the study and a list of subjects who experienced SAEs will also be provided.

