11.1 Schedule of Evaluations and Procedures

11.1.1 Visit 1: Screening Visit (Day -35 to Day 0)

The following procedures will be conducted at this visit:

- 1. Obtain written informed consent prior to performing any study procedures. Subjects less than the age of consent must sign an assent form, and the parent or legal guardian must sign the informed consent form.
- 2. Assign the subject a 6-digit subject number by accessing RTSM. The number will consist of the 3-digit study center number (pre-assigned to your study center) and the 3-digit sequential order screening number assigned by the RTSM (eg, 101001, 101002; in this example study center number is 101).
- 3. Record the subject's demographic information.
- 4. Record the subject's medical history.
- 5. Record all previous medications (including acne medications) used for the past 4 weeks (past 6 months for systemic retinoids). Record any therapies that will be used concomitantly during the study.
- 6. Perform an abbreviated physical examination, including height and weight, and measure vital signs (blood pressure, heart rate, respiration rate, and oral temperature). Note: height will only be measured at Screening, and not at subsequent study visits.
- 7. Assess the subject using the EGSS, followed by inflammatory and non-inflammatory lesion counting to determine eligibility.
- 8. Perform a urine pregnancy test for all females who are premenses and FOCBP. The urine pregnancy tests will be supplied by the CRO/designee.
- 9. Verify that the subject meets the applicable inclusion/exclusion criteria as outlined in Sections 8.1 and 8.2.
- 10. Discuss allowed cleansers, moisturizers, and sunscreens, and record any cleanser, moisturizer, and sunscreen use (Appendix 17.2).
- 11. If subject wears makeup, remind the subject not to wear makeup during any future visits.
- 12. If the subject requires a washout, schedule the Baseline visit to occur after the washout is complete. If no washout is required, the Screening and Baseline visits may occur on the same day.
- 13. Schedule the subject to return for the Baseline/Day 0 visit. If the subject requires a washout, schedule the Baseline/Day 0 visit to occur after the washout is complete.

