11.4 Adverse Events

11.4.1 Definition of Adverse Event

An AE is any untoward medical occurrence in a patient or clinical investigation subject administered a medicinal product and which does not necessarily have a causal relationship with the study drug. AEs include any unfavorable and unintended illness, sign, symptom, clinically significant laboratory test abnormality, or disease temporally associated with the use of a medicinal product that has appeared or worsened during the course of the clinical trial, regardless of causal relationship to the study drug(s) under study. The collection of AEs will begin following the subject's completion of the consent process to participate in the study.

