11.4.2 Documenting Adverse Experiences

It is the responsibility of the investigator to document all AEs that occur during the course of the study. The AEs should be documented as a single medical diagnosis. When this is not possible, the AE should be documented in terms of signs and/or symptoms observed by the investigator or reported by the subject at each study visit. Each AE which appears to be independent of any prior event will be reported separately.

All AEs occurring after the subject signs the informed consent through the last study visit must be reported, regardless of whether or not the AEs are considered study drug-related. All AEs, whether in response to a query, observed by the study center personnel, or reported spontaneously by the subject, will be recorded. Any AEs deemed related to treatment reported or observed at the final study/treatment visit will be followed until stabilization or resolution.

At each visit during the study, the subject will be assessed for the occurrence of new and ongoing AEs. Cutaneous safety and tolerability signs and symptoms that result in the subject's requiring a concomitant therapy, interruption of treatment, or discontinuation from the study will be reported as an AE. The following data will be collected on all AEs and recorded on the appropriate eCRF:

- Event description (diagnosis preferred, if unknown, record the signs/symptoms)
- Onset date and end date
- Maximum intensity (severity)
- Seriousness
- Action taken regarding study drug
- Corrective treatment, if given
- Outcome

In addition, the investigator's assessment of causality will be recorded.

Vital sign and laboratory abnormalities are to be recorded as AEs only if they are clinically significant (for example: are symptomatic, requiring corrective treatment, increased monitoring, leading to discontinuation or fulfilling a seriousness criterion).

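### The TEAE definition has no worsening clause, and the Fisher's exact comparison is worded for all AEs since consent instead of TEAEs (minor)

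*Combined protocol and SAP*

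**What the plan says.** Section 12.2.1 defines the term by date alone: "Treatment-emergent adverse events (TEAEs) are those events with an onset on or after the date of the first study drug application". It then plans TEAE summaries by number of subjects, system organ class, preferred term, severity, seriousness and relationship. The next paragraphs describe severity and relationship tables for adverse events, and a summary of AEs reaching 5% in any group, without repeating the TEAE restriction. Of that last summary it says: "The percentage of subjects for each treatment group will be compared using a Fisher's Exact test". The synopsis likewise applies the Fisher test to subjects reporting any adverse event, at the 0.05 level.

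Section 11.4.1 is wider. An AE is an event "that has appeared or worsened during the course of the clinical trial", and "The collection of AEs will begin following the subject's completion of the consent process to participate in the study". Section 11.4.2 agrees: "All AEs occurring after the subject signs the informed consent through the last study visit must be reported". The screening window is given by the heading of Section 11.1.1, "Visit 1: Screening Visit (Day -35 to Day 0"). Screening and Baseline may fall on the same day if no washout is needed.

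On recording, Section 11.4.2 asks for onset and end dates and "Maximum intensity (severity") for each AE, and for a separate report only when an AE appears independent of any prior event. Section 11.4.4 assigns each AE its maximum severity. The visit procedures in Section 11.1 ask sites to record changes in ongoing AEs.

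**The concern.** There are two separate gaps, and they affect different outputs.

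The first concerns the TEAE summaries. An event that starts during washout and becomes worse on study drug keeps its pre-dose onset date, so the rule in Section 12.2.1 excludes it. The plan gives no rule for a new record or a new date when an ongoing AE worsens. Washout subjects are stopping topical retinoids, corticosteroids and anti-acne products, so a skin event in this window is plausible.

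The second concerns the between-arm test. Read literally, it includes events that occurred before any study drug was applied. Randomization takes place at Baseline, so in expectation these events add equally to every arm and pull the arms together. The study's stated purpose includes comparing the safety of IDP-126 Gel with Epiduo Forte and vehicle. Movement toward no difference is the unhelpful direction there, because it can hide a real excess.

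**Working it through.** **Step 1: the worsening gap, by reading the rules together.** Take an AE with onset after consent and before first application, mild at onset and severe on treatment.
- Section 11.4.1: it is an AE.
- Section 11.4.2: the worsening is not independent of the prior event, so nothing requires a separate record.
- Section 11.4.4: the recorded severity is the maximum, here severe.
- Section 12.2.1, TEAE rule: onset precedes first application, so it is not a TEAE and leaves the TEAE summaries.
- Section 12.2.1, all-AE tables and listings: it is included as severe, with onset shown relative to first dose.

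**Step 2: dilution of the Fisher comparison.** The documents give no AE rate, no pre-dose AE rate and no power for this test, so there is no plan figure to reproduce.

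Inputs from the documents: 220 subjects for IDP-126 Gel and 220 for Epiduo Forte (Section 12.8.1); the two vehicle arms of 110 combined for analysis, giving 220 (Section 12); alpha 0.05 (synopsis).

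Assumptions: pairwise comparisons; true on-treatment probabilities p1 and p2; a pre-dose probability q, equal in all arms and independent of on-treatment events.

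Observed probability = 1 − (1 − q)(1 − p). Observed difference = (1 − q)(p1 − p2).

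Exact power of the two-sided Fisher test, 220 vs 220, alpha 0.05:

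| Assumed case | q | Observed rates | Difference (points) | Risk ratio | Power |
|---|---|---|---|---|---|
| One preferred term, 10% vs 3% | 0 | 10.0% vs 3.0% | 7.00 | 3.33 | 82.4% |
| | 1% | 10.9% vs 3.97% | 6.93 | 2.75 | 75.8% |
| | 2% | 11.8% vs 4.94% | 6.86 | 2.39 | 69.8% |
| | 5% | 14.5% vs 7.85% | 6.65 | 1.85 | 55.3% |
| Any AE, 30% vs 18% | 0 | 30.0% vs 18.0% | 12.0 | 1.67 | 81.6% |
| | 2% | 31.4% vs 19.6% | 11.8 | 1.60 | 78.2% |
| | 5% | 33.5% vs 22.1% | 11.4 | 1.52 | 73.1% |
| | 10% | 37.0% vs 26.2% | 10.8 | 1.41 | 64.9% |

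For a preferred term, q is the pre-dose probability of that same term; for any AE, it is the pre-dose probability of any event.

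For a rare term, power falls more than the difference does because the added events also raise the variance. At q = 0, p1(1 − p1) + p2(1 − p2) = 0.0900 + 0.0291 = 0.1191, so the standard error is √(0.1191/220) = 0.0233 and the ratio 0.070/0.0233 is about 3.0. At q = 5% the sum is 0.1240 + 0.0723 = 0.1963, the standard error is 0.0299 and the ratio 0.0665/0.0299 is about 2.2.

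**Step 3: Type I error.** With a true rate of 25% in both arms, the Fisher rejection rate is about 3.9% at q = 0, 5% and 10%. It is not inflated.

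**The case against.** The case for treating this as small is strong, and most of it stands.

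- A reader might infer that on-drug worsening is lost altogether. It is not: Step 1 shows that the event leaves only the TEAE summaries. The gap is also confined to AEs starting between consent and first application. A condition present before consent that worsens on drug is itself an AE under Section 11.4.1, and would be a TEAE if onset is dated at the worsening, though the plan does not say how to date it.
- For the main local risks there is a second source. Scaling, erythema, pigmentation changes, itching, burning and stinging are scored 0 to 3 at Baseline and at each later visit (Sections 11.3.1 and 11.3.2). Section 12.2 tabulates grade 3 reactions after first application, and the synopsis limits its cutaneous AE measure in the same way. These scores do not cover other AEs and do not repair the TEAE tables.
- A reader might infer that severity and relationship are never summarized for TEAEs. Section 12.2.1 already plans both; only the Fisher test lacks a TEAE counterpart.
- A reader might infer that the worsening could never be reconstructed. Sites record changes in ongoing AEs, and the eCRF layout is not in the documents, so that cannot be established.
- A large power loss is tempting to quote. Giving every subject 35 pre-dose days at the lower arm's on-drug rate yields q = 1 − 0.8^(35/84) = 8.9%; 30% vs 20% becomes 36.2% vs 27.1%, and power falls from 64.2% to 49.9%. The documents do not support that premise. Most listed washouts are 1 to 4 weeks, and subjects needing none may start on the screening day.
- AEs in the Fisher sentence may be loose wording for TEAEs, and Section 12 promises a separate SAP that could settle it. The protocol does not say so, however, and elsewhere it states the after-first-application limit explicitly.

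**Conclusion.** The point holds in a limited form and is minor. The TEAE definition is narrower than the plan's own AE definition and leaves out consent-to-dose events that worsen on drug, but only from the TEAE summaries. As worded, the Fisher comparison includes pre-dose events, which shrinks any true difference by (1 − q). The direction follows from arithmetic, given equal and independent pre-dose risk; the size does not, because neither q nor the AE rates are in the documents. Under the assumed rates the power loss runs from about 3 points (any AE, q = 2%) to about 27 points (one preferred term, q = 5%). It is negligible if few subjects have a washout period or few pre-dose events occur. No figure in the plan is contradicted.

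A reader might also infer a real problem from the calendar-date rule, since a Day 0 event before the first application counts as treatment-emergent. That affects part of one day and errs toward counting events, so it does not add to the concern.

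**What to change.** 1. In Section 12.2.1, define a TEAE as an AE with onset on or after the first application of study drug, or one present before it that increases in severity after it.
2. In Section 11.4.2, state that a post-dose increase in severity of a pre-dose AE is recorded with its own date. This belongs in the recording rules because it governs data collection and should not wait for the SAP.
3. In Section 12.2.1 and the synopsis, state that the Fisher's exact comparison uses TEAEs in the safety set, and list pre-treatment AEs separately.

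A before/after first application flag for Day 0 events is optional.

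The cost is a wording change in three places and a few extra AE records for worsening events. Neither the sample size nor the efficacy analysis changes.

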12.2.2 Safety Laboratory Tests

Changes from baseline in safety laboratory values will be summarized with descriptive statistics at all applicable study visits. Shift tables will be presented for changes in safety laboratory values. Normal ranges established by the central laboratory will be used to determine the shifts. A listing of all out-of-range laboratory test results at any assessment time point will also be

CONFIDENTIAL

provided. Determination of clinical significance for all out-of-range laboratory values will be made by each investigator and included in the listing. In addition, a listing of all clinically significant laboratory test results will be provided.

12.2.3 Vital Sign Measurements

Changes from baseline in vital sign measurements will be summarized with descriptive statistics for each treatment group at all applicable study visits. In addition, shifts in vital sign results (normal to abnormal, abnormal to normal, etc., based on the normal ranges) from Baseline to Week 12 (or ET) will be summarized using shift tables.

Individual vital sign test results will be presented in a by-subject listing. A listing of all out-of-range vital sign measurements at any assessment time point will also be provided.

12.2.4 Concomitant Medications

All recorded prior and concomitant medications will be classified based on terminology from the World Health Organization (WHO) Drug Dictionary. Therapies and medications data will be presented in data listings.

12.3 Subject Disposition

A tabulation of subject disposition will be provided. The tabulation will include the numbers of subjects who enter the study, complete the study, and discontinue the study. The reasons for discontinuation will be included.

12.4 Demographics and Baseline Characteristics

Subject demographic and baseline characteristics will be summarized by study drug group using both the ITT, PP, and the Safety analysis sets. For continuous variables (eg, age), comparisons among the 3 study drug groups will be conducted using a two-way analysis of variance with factors of treatment and analysis center. Ethnicity and race will be analyzed with a Cochran-Mantel-Haenszel stratified by analysis center. Past and current medical conditions, as well as history of disease, will be presented in data listings and not be compared statistically.

12.5 Protocol Deviations

All protocol deviations will be reported to the Sponsor and recorded throughout the study. A tabulation of protocol deviations will be included in a data listing.

12.6 Compliance

The number and percentage of subjects who are compliant in each treatment group will be summarized descriptively. Subjects may not miss more than five consecutive days of dosing and must take 80-120% of expected doses to be considered compliant. The number of expected doses will be determined for each subject based on the length of their participation in the study and will

be capped at 89 days; the number of planned doses given a subject attended the Week 12 visit on the latest day within window.

12.7 Interim Analyses

No interim analyses are planned.

12.8 Additional Statistical Considerations

12.8.1 Analysis Sets

Approximately 660 subjects at least 12 years of age and older with moderate or severe acne (a score of 3 or 4 [moderate to severe] using the EGSS) will be enrolled and randomized in the study. With a 2:2:1:1 randomization ratio, it is anticipated that:

- 220 subjects to receive IDP-126 Gel, once daily application
- 220 subjects to receive Epiduo® Forte Gel, once daily application
- 110 subjects to receive IDP-126 Vehicle Gel (stored at 2-8°C), once daily application
- 110 subjects to receive IDP-126 Vehicle Gel (stored at CRT), once daily application

The ITT analysis set will consist of all randomized subjects who received study drug. The safety analysis set will be comprised of all randomized subjects who are confirmed to have dosed at least once.

An ITT analysis will be conducted, as well as a PP analysis. Subjects will be eligible for the PP analysis if they complete the 12-week evaluation without noteworthy study protocol violations (i.e., any subject or investigator activity that could have possibly interfered with the therapeutic administration of the study drug or the precise evaluation of study drug efficacy). The PP analysis set will include subjects in the safety analysis set who do not meet any of the following criteria:

- Failed any of the inclusion/exclusion criteria.
- Have taken any interfering concomitant medications.
- Did not attend the Week 12 visit.
- Missed more than 1 post baseline study visit prior to Week 12.
- Have not been compliant with the dosing regimen (i.e., subjects may not miss more than 5 consecutive days of dosing and must take 80%-120% of expected doses; the number of expected doses will be determined for each subject based on the length of their participation in the study).
- Out of visit window at the 12-week visit.

Subjects who discontinue from the study due to an adverse event related to study treatment or documented lack of treatment effect (and/or worsening of condition) will be included in the PP population. Prior to breaking the blind, other additional criteria may be added to the list to

accommodate for unforeseen events that occurred during the conduct of the study that result in noteworthy study protocol violations.

12.8.2 Sample Size Determination

Power calculations are based primarily on the Week 12 results of the Phase 2 study, V01-126A-201. This study was a five-arm study including IDP-126 Gel versus each of the dual components and Vehicle Gel. Furthermore, Component A (BPO 3.1%/adapalene 0.15%) is considered the component of IDP-126 which is analogous to Epiduo®, and Epiduo® indicated nearly identical reduction in non-inflammatory lesions to Epiduo® Forte Gel. Using estimates from the V01-126A-201 study for Component A and IDP-126 Vehicle Gel to define the non-inferiority margin and for power calculation assumptions allows for the use of estimates within one study thus avoiding comparisons between different studies which are under different timeframes and different conditions.

A total of approximately 660 randomized subjects are planned for this study, including 220 subjects each in the IDP-126 Gel and Epiduo[®] Forte Gel groups, and 110 subjects each in the IDP-126 Vehicle Gel groups, based on the results of the IDP-126A study as below.

V01-126A-201 Results						
		IDP-126	IDP-126 Component A	IDP-126 Vehicle		
		(N=146)	(N=150)	(N=148)		
Inflammatory Lesions	LSMean (SD)	29.9 (11.9)	26.7 (11.7)	19.6 (12.1)		
Non-Inflammatory Lesions	LSMean (SD)	35.5 (16.3)	29.9 (16.4)	21.8 (16.6)		
EGSS	Success (%)	52.5	27.8	8.1		

A sample size of 220 for the IDP-126 group and 220 for the combined Vehicle Gel group has greater than 95% power to detect a statistically significant difference in Inflammatory Lesions, Non-Inflammatory Lesions, and in the percentage of subjects who have at least a 2 grade reduction at Week 12 from baseline in EGSS and were Clear or Almost Clear with a significance level of 0.05.

A sample size of 220 for the IDP-126 group and 220 for the Epiduo® Forte Gel group has greater than 95% power to detect non-inferiority of Inflammatory Lesions, Non-Inflammatory Lesions, and in the percentage of subjects who have at least a 2 grade reduction at Week 12 from baseline in EGSS and were Clear or Almost Clear with a significance level of 0.05.

A sample size of 220 for the IDP-126 group and 220 for the Epiduo® Forte Gel group has greater than 95% power to detect a statistically significant difference in the percentage of subjects who have at least a 2 grade reduction at Week 12 from baseline in EGSS and were Clear or Almost Clear with a significance level of 0.05. Additionally, this provides approximately 80% power to detect a statistically significant difference in Inflammatory Lesions and greater than 90% power to detect a statistically significant difference in Non-Inflammatory Lesions based on a two-sided t-test and a significance level of 0.05.

